**Please note:**

- 1 month corresponds to 30 days
- Study visits should occur as close as possible to the specified time points in the protocol, but time windows are permitted as specified in the SoA
- At any scheduled or unscheduled visit, the dose of study intervention may be increased to the next possible higher dose, based on serum/plasma potassium level analyzed in the local laboratory and provided the participant was already on a stable dose for 4 weeks ±7 days.

Abbreviations: AE = adverse event; CKD-EPI = Chronic Kidney Disease Epidemiology Collaboration; D = Day; eGFR = estimated glomerular filtration rate; ECG = electrocardiogram; EOS = end-of-study; EQ-5D-5L = EuroQoL Group 5-dimension 5-level questionnaire; hs-TnT = high-sensitivity troponin-t; IxRS = interactive voice / web response system; med. = medication; KCCQ = Kansas City Cardiomyopathy Questionnaire; M = Month; NT-proBNP = n-terminal prohormone B-type natriuretic peptide; NYHA = New York Heart Association; O = on-site; PGIC = Patient Global Impression of Change; PGIS = PGI of Severity; PD = premature discontinuation; PT = post-treatment; SoA = schedule of activities; Tel. = telephone

- Randomization has to occur within 2 weeks of the Screening Visit. If the Screening Visit and Visit 1 (Day 1, Baseline) are performed on the same day, procedures listed for both visits are to be performed only once.
- Study visits to be conducted as a clinic visit or a telephone contact visit. These visits will alternate at 4-monthly intervals from Month 12 onwards with participant contact being made every 2 months.
- This visit should be performed for safety check after any up-titration (4 weeks ±7days) and after restart of study intervention following an interruption for >7 consecutive days. A full unscheduled safety visit should be performed within an adequate timeframe proposed by the investigator after down-titration for reasons other than hyperkalaemia, otherwise only potassium is to be rechecked (refer to [Table 6–1](#))

- d The PD Visit should take place as soon as possible but within 7 days after the last intake of study intervention. If the PD Visit cannot be performed within the timeframe specified, no PD Visit is required. All randomized participants will be followed until the study ends, even if they did not take study intervention or permanently discontinued study intervention.

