There are uncertainties associated with the responsiveness of NT-proBNP to MRAs. No *quantitative* prediction as to the changes of NT-proBNP for different finerenone doses were performed with an exposure/response model built on ARTS-HF data for finerenone in HFrEF patients. However, from a *qualitative* perspective, a linear exposure response from 2.5 mg up to 20 mg has been observed in the ARTS-HF trial indicating that NT-proBNP response was not saturated at 20 mg. This would suggest the possibility of greater effects on NT-proBNP at doses higher than 20 mg.

40 mg OD is the maximum maintenance dose of finerenone in patients with eGFR >60 mL/min/1.73 m^2. When the expected systemic finerenone exposure in these patients with mild renal impairment or normal renal function is compared with observed data in patients with moderate renal impairment receiving finerenone 20 mg in ARTS-HF, largely overlapping exposures are noted due to the effect of moderate renal impairment on area-under the curve (AUC; about 50% increase). These considerations on exposure in patients receiving 40 mg are complemented by exposure/response (PK/pharmacodynamics) analyses and simulations based on data from ARTS-HF. Changes in serum potassium and eGFR from baseline following administration of finerenone 40 mg to patients with normal renal function or mild renal impairment were also estimated to largely overlap with changes following administration of finerenone 20 mg to patients with moderate renal impairment. Generally, the drug effect on serum potassium and eGFR is estimated to be rather small even for 40 mg, compared to the impact of baseline values of the respective parameters. Based on model simulations, the expected change in steady-state serum potassium and eGFR following administration of finerenone 10, 20 and 40 mg OD to the HF population is an increase by 0.1, 0.2 and 0.2 mmol/L and a decrease by 2.4, 3.1 and 3.8%, respectively.

The safety of the 40 mg dose in patients with an eGFR >60 mL/min/1.73 m^2 will also be ensured by the starting dose of 20 mg with escalation to 40 mg only after measuring serum potassium and eGFR levels, and the possibility of down-titration.

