### 6.1 Study Intervention(s) Administered

The IxRS will determine the medication numbers for the study site investigator or designee to select for the participant.

Eligible participants will receive study intervention at the doses illustrated in [Table 6-1](#), dispensed as outlined in the SoA (Section [1.3](#)). The dose of finerenone will depend on the eGFR value at the Baseline Visit (determined by the local laboratory):

1. Participants with an eGFR  $\leq 60$  mL/min/1.73m^2 will start with 10 mg (dose level 1) and have a maintenance dose of 20 mg (dose level 2). Dose level 1 is the minimum dose and dose level 2 is the maximum permitted dose in this group of patients
2. Participants with an eGFR  $>60$  mL/min/1.73m^2 will start with 20 mg (dose level 2) and have a maintenance dose of 40 mg (dose level 3). Dose level 1 is the minimum dose and dose level 3 is the maximum permitted dose in this group of patients.

The investigator is encouraged to up-titrate the dose of study intervention once the participant has been on a stable dose for 4 weeks ( $\pm 7$  days), either at the next regular visit or at an Up-titration Visit (see [Table 6-1](#)). Participants who do not tolerate their starting dose of 20 mg may be down-titrated at any point during the study, including between-scheduled visits if required for safety reasons. These participants may be up-titrated again based on the rules provided in [Table 6-1](#). If the participant is already at the minimum dose, the study intervention can be interrupted at the investigator's discretion as detailed in Section [6.6](#), based on blood potassium levels and renal function which will be monitored throughout the study.

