**Table 6–1 Dosage of Study Intervention for Administration**

eGFR value at the Baseline Visit, based on local laboratory results:	eGFR 25 to ≤60 mL/min/1.73m 		eGFR >60 mL/min/1.73m 	
Participant randomized to group:	Finerenone	Placebo	Finerenone	Placebo
Starting dose:	10 mg finerenone OD	Placebo OD (Dose Level 1)	20 mg finerenone OD	Placebo OD (Dose Level 2)
Maintenance dose:	20 mg finerenone OD	Placebo OD (Dose Level 2)	40 mg finerenone OD	Placebo OD (Dose Level 3)
Minimum dose after down-titration:	10 mg finerenone OD	Placebo OD	10 mg finerenone OD	Placebo OD
Maximum dose after up-titration:	20 mg finerenone OD	Placebo OD	40 mg finerenone OD	Placebo OD
Study intervention intake	One tablet of study intervention OD, preferably in the morning at approximately the same time each day. Note: Study intervention will be administered at home, except on the day of the first PK visit when the tablet will be taken at the study site			
Missed intake	
 
If discovered within 16 hours after the scheduled time, the participant should take one tablet of study intervention as soon as possible
 
If discovered >16 hours after the scheduled time, this will be considered to be a 'missed' dose and the participant should wait and take the next tablet of study intervention at the usual (scheduled) time.
 
			
Up-titration of dose	
Finerenone
 
 
Up-titrate study intervention to the next possible higher dose based on serum/plasma potassium level
 
eGFR decrease is <30% compared to last scheduled visit.
 
 
Placebo
 
 
Sham-titrate.
 
			
Down-titration of dose	
 
If potassium ≥5.5, down-titrate to the next lower dose level in a step-wise manner (dose level 2 to 1, or dose level 3 to 2)
 
If at dose level 1, interrupt study intervention treatment; study intervention should be re-introduced at dose level 1 as soon as the investigator considers it to be medically justified without compromising safety
 
If in the opinion of the investigator, the participant cannot tolerate the maximum dose level of study intervention, the study intervention dose may be reduced to the next lower dose level.
 
			

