**Table 6–2 Potassium Levels and Guidance for Dose Adjustment**

Serum / plasma potassium (K + mmol/L)	Action to be taken
First sample:	
<5.0	Increase to the next higher dose level (or continue at maximum permitted dose level)
≥5.0 to <5.5	Continue the current dose level
≥5.5 to <6.0	Down-titrate to the next lower dose if possible; if patient is already on dose level 1, interrupt study intervention. K + should be re-checked within 72 h of initial K + result awareness; follow option a
≥6.0	Interrupt study intervention and K + should be re-checked within 72 h of initial K + result awareness; follow option b
Second and subsequent sample:	
Option a <5.5	Continue current dose
≥5.5	Down-titrate to the next lower dose if possible, or interrupt study intervention and recheck K +
Option b <5.5	Restart at dose level 1
≥5.5	Continue to withhold study intervention, further monitoring of K + . Restart at dose level 1 ONLY if K + is <5.0 mmol/L

The following aspects have also to be taken into consideration:

1. If the participant is already on dose level 1 no further decrease is possible after interruption, the same dose level should be re-started once serum/plasma potassium falls below 5.5 mmol/L. Serum/plasma potassium is to be measured at a safety visit 4 weeks ± 7 days after re-starting treatment or dose adjustment.
2. If the participant is on dose level 1 of study intervention, but hyperkalemia recurs soon after a previous event of hyperkalemia leading to interruption of study intervention, and there is no explanation for the recurring hyperkalemia event other than intake of study intervention, premature and permanent discontinuation of study intervention is recommended.
3. In case of hyperkalemia, it is at the investigator's discretion to take measures, including treatment and monitoring in accordance with local practice standards, beyond those reflected in [Table 6–2](#).

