## 7. Discontinuation of Study Intervention and Participant Discontinuation/Withdrawal

### 7.1 Discontinuation of Study Intervention

After randomization, discontinuation of study intervention (for any reason) does not constitute the participants' withdrawal from the study (see also Section [7.2](#)).

Study intervention must be prematurely and permanently discontinued if any of the following occurs:

- Pregnancy of the participant (see also Section [8.3.5](#))
- The investigator is of the opinion that continuation of treatment with study intervention is harmful to the participant's well-being
- The randomization code is broken by the investigator, or other responsible person, when knowledge of the participant's treatment is required
- Any investigational drug other than the study intervention is used.
- Treatment with an MRA (eplerenone, spironolactone, canrenone, esaxerenone) for a period of more than 2 weeks.

Study intervention *may* be prematurely and permanently discontinued if any of the following occurs:

- Any suspected drug-related AE or SAE
- If any exclusion criterion applies during treatment
- If a significant violation of the protocol occurs, as defined by the sponsor and the coordinating investigator.

Participants who prematurely and permanently discontinue study intervention are expected to continue in the post-treatment follow-up period and to attend all protocol-specified study visits, and should be encouraged to perform all scheduled assessments described in the SoA for premature discontinuations ([Figure 1–2](#)).

Under certain circumstances, should the reason for permanent discontinuation of study intervention change, making it no longer applicable and the investigator is of the opinion it is in the subject's best interest to restart treatment, study intervention may be restarted on a case-by-case basis following comprehensive review by the Study Medical Expert.

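### Table 6–2 interrupts drug at a first K+ ≥6.0 mmol/L, but lets a participant who was on 40 mg continue at 10 mg when a re-check reaches ≥6.0

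*Protocol*

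**What the plan says.** For a first sample, Table 6–2 in Protocol Section 6.6.1 has two bands at or above 5.5 mmol/L.

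- **5.5 to <6.0:** step down one dose level, or interrupt if already on level 1; re-check within 72 h; follow option a.
- **≥6.0:** interrupt, with no condition on dose level; re-check within 72 h; follow option b.

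For the second and later samples, option a has only <5.5 (stay on the current dose) and ≥5.5: "Down-titrate to the next lower dose if possible, or interrupt study intervention and recheck" potassium. Option b at ≥5.5 keeps the drug withheld until potassium is below 5.0.

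The down-titration row of Table 6–1 has no ≥6.0 band either: "If potassium ≥5.5, down-titrate to the next lower dose level in a step-wise manner". At level 1 it calls for interruption.

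Only participants with baseline eGFR >60 can be on 40 mg. For them, Section 6.1 states: "Dose level 1 is the minimum dose and dose level 3 is the maximum permitted dose in this group of patients".

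On follow-up, footnote c to the Schedule of Activities asks for a full safety visit "after down-titration for reasons other than hyperkalaemia, otherwise only potassium is to be rechecked". It gives no time limit for that potassium re-check.

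**The concern.** The same potassium value gets a different rule depending on when it is seen. As a first value, ≥6.0 means drug off at any dose. As a re-check after a step down from 40 mg, it may be met with another step down. That second participant's potassium has risen despite a dose cut, so the looser rule falls on the worse course. Option b shows the contrast: a participant already off drug whose re-check is only 5.5–5.9 may not restart even at 10 mg until potassium is below 5.0.

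Hyperkalemia is the drug's important identified risk (Protocol Section 2.3), and Section 9.4.2 classes ≥6.0 as severe. At stake is dosing safety in a narrow group. Power, type I error and the efficacy analyses are not involved.

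**Working it through.** The plan states no figure on this point, so the check traces the table's rules.

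**Inputs.** Three dose levels (10, 20, 40 mg; Table 6–1); two first-sample bands (5.5 to <6.0 and ≥6.0; Table 6–2); three re-check bands (<5.5, 5.5 to <6.0, ≥6.0).

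**Paths.** 3 × 2 × 3 = 18 in all, of which 3 × 2 × 1 = 6 have a re-check ≥6.0:

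| Level at first sample | First K+ 5.5 to <6.0 | then re-check ≥6.0 | First K+ ≥6.0 | then re-check ≥6.0 |
|---|---|---|---|---|
| 1 (10 mg) | interrupt | stays off drug | interrupt | withhold |
| 2 (20 mg) | step to 10 mg | no lower dose: interrupt | interrupt | withhold |
| 3 (40 mg) | step to 20 mg | step to 10 mg, **drug continued**, or interrupt | interrupt | withhold |

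Drug may continue on 1 of the 6 paths and is off on the other 5. The count is the same whether the "or" in option a is read as a free choice or as a fallback when no lower dose exists. Under the fallback reading, the step to 10 mg is what the row directs.

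**Next sample on the exposed path.** Option a's rows also govern later samples. The participant is now on level 1. A value <5.5 means staying on 10 mg. A value ≥5.5 leaves no lower dose, so both tables call for interruption. The extra exposure is therefore one re-check interval at 10 mg.

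**Length of that interval.** The row asks for a re-check without a deadline. The only dated test in Section 6.6.1 after a dose adjustment is the safety visit in note 1, at 4 weeks ± 7 days, so at most 28 + 7 = 35 days. In practice a site could act anywhere between the 72 h used for first samples and that visit.

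**Modelled drug effect.** Section 4.3 says the expected steady-state potassium change at 10, 20 and 40 mg "is an increase by 0.1, 0.2 and 0.2 mmol/L". Stopping rather than continuing 10 mg therefore gains on average 0.1 − 0 = 0.1 mmol/L (0.05 to 0.15 allowing for rounding). These are population means and do not describe participants whose potassium has already reached 6.0.

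**The case against.** The strongest reply is that the investigator can already interrupt. The row offers it, the Synopsis (Section 1.1) allows it at any time for safety, note 3 under Table 6–2 permits measures beyond the table, and the table is titled guidance. All of that stands. It shows that interruption is allowed on this path; the sponsor nevertheless wrote an explicit interruption row for a first ≥6.0, and no row or note carries it over to a re-check ≥6.0.

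Second, the group is probably small. Section 4.3 reports that values above 6 in the earlier heart failure study occurred mainly with eGFR ≤60 and UACR >300, and participants with baseline eGFR ≤60 are capped at 20 mg. This also stands, as does the independent DMC's safety review.

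Some stronger readings are tempting and should be resisted.

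- *A reader might infer that drug could continue indefinitely with no potassium value ever stopping it.* The next sample at ≥5.5 leads to interruption at level 1.
- *A reader might take Section 7.1 as the interruption rule*, because it applies when the investigator thinks "continuation of treatment with study intervention is harmful" to the participant. That section concerns permanent discontinuation.
- *A reader might say the benefit-risk section is contradicted.* Section 2.3 names dose reduction among its potassium safeguards, and the dose does fall on this path.
- *A reader might think only option a lacks a deadline.* Option b's ≥5.5 row has none either, although those participants are off drug.
- *1 of 6 is not a frequency.* It counts unweighted paths.

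**Conclusion.** The inconsistency is real and narrow. At a re-check ≥6.0, Table 6–2 permits continued dosing for one group only: participants on 40 mg whose first value was 5.5–5.9. The excess is one further re-check interval at 10 mg, with no deadline in the row. Interruption is permitted at that value but not called for.

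This rests on reading the re-check as a later sample under option a, which is where the table places it. Treating it as a new first sample would close the gap, but nothing in the documents says to do so. The number of participants affected cannot be derived, and no endpoint analysis is affected. The point deserves correction because the change is cheap and concerns the drug's main known risk; the documents do not establish a quantified harm.

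**What to change.** Split option a's ≥5.5 row in Table 6–2 into two:

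1. **≥5.5 to <6.0:** step down if a lower dose exists, otherwise interrupt; re-check potassium within 72 h.
2. **≥6.0:** interrupt at any dose level; re-check within 72 h; follow option b.

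Amend the down-titration row of Table 6–1 to cover 5.5 to <6.0, with interruption at ≥6.0; otherwise the two tables would still disagree. Under these rows drug continues at a re-check ≥6.0 on 0 of the 6 paths.

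The cost is edits to two tables, a clarification to sites, and a few more temporary interruptions among participants on 40 mg. Restart also becomes stricter for some: under option b, if the next value is still ≥5.5, drug waits for potassium below 5.0 instead of the 5.5 in note 1. Because the new row applies at any level, that threshold would also reach participants who began the sequence on 20 or 10 mg and are already off drug at that point.

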## 6.6 Dose Modification

As described in Sections [6.6.1](#) and [4.3](#), the dose of study intervention should be adjusted (up-or down-titration) on the basis of potassium and eGFR levels.

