If a participant no longer on study intervention is unable to attend the clinic for a study visit, a telephone consultation may be performed to determine if relevant health events /endpoints (e.g. development of CV or renal complications) have occurred. Ideally, a face-to-face visit should be performed at least once a year. The End of Study (EOS) visit is expected to be an onsite visit and should not be replaced by a telephone consultation unless an onsite visit is not feasible. Expected frequency of telephone contacts should be in line with the standard visit schedule, and therefore performed every 4 months. Ad hoc additional telephone contacts may also be requested (e.g. prior to the interim analysis) and made to the participant themselves or to other contact as provided by the patient, e.g. next of kin, primary physician (or local equivalent).

Note that study intervention may be temporarily discontinued (i.e. interrupted), as described in [Section 6.6](#).

See the SoA ([Section 1.3](#)) for data to be collected at the time of intervention discontinuation and follow-up and for any further evaluations that need to be completed.

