### 7.1.1      **Temporary Discontinuation**

#### **Resumption of study intervention after temporary interruption**

Upon temporary interruption of the study intervention due to hyperkalemia, eGFR decrease, (S)AE, outcome events (OE), intolerance or any other reason, intake should be resumed as soon as medically acceptable at the discretion of the investigator. There is no defined maximum time limit for temporary interruption. In all cases, the reason for study intervention interruption must be recorded in the eCRF and the participant's medical records.

If the study intervention is interrupted for more than 7 days, the re-start should be performed at the next lower dose and the investigator should schedule an up-titration visit after 4 weeks ( $\pm$  7 days) in order to monitor potassium levels and renal function (see [Table 6–1](#)). If a regular visit will be scheduled to take place 4 weeks  $\pm$  7 days after up-titration or re-start, the monitoring of potassium and renal function is assured and no up-titration visit has to be performed in addition. A restart and/or safety check visit is expected only if the investigator is aware of a temporary interruption that was initiated by the study participant.

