### Local Laboratory Assessment

Blood safety samples will be taken from the Screening Visit onwards for analysis at the local laboratory.

- The following clinical chemistry parameters must be measured and the values documented in the eCRF
  - Serum/plasma creatinine (eGFR will be calculated automatically in the eCRF using the CKD-EPI formula)
  - Serum/plasma potassium.

From visit 2 (Month 1) onwards, study participants may have their local laboratory assessments taken up to 3 days prior to the study visit.

Potassium values should be recorded using a single decimal point (e.g. 4.5 mmol/L or mEq/L). In the event of hyperkalemia, please see [Table 6–2](#) for guidance.

Up-titration or down-titration of the study intervention will be based on local potassium results and must be documented in the eCRF. Down-titration of the study intervention should occur primarily for safety reasons but can also be done for exceptional logistical reasons (e.g. study intervention supply issue).

Additionally, at screening, BNP or NT-proBNP can be measured if not available from clinical medical records.

In women of childbearing potential, a pregnancy test will be performed locally, at screening and baseline. Further pregnancy tests should be performed in participants of childbearing potential as required by national/institutional regulations (e.g. at every visit). At any time during study participation, additional pregnancy testing should be performed upon suspicion of pregnancy. Both serological and urine tests are acceptable.

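### After an interruption for potassium of 6.0 mmol/L or more, the protocol gives two restart doses from level 3 (off drug more than 7 days) and, on one reading, two restart thresholds at level 1

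*Protocol*

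**What the plan says.** **Protocol Section 6.6.1, Table 6-2.** A first potassium value of 6.0 mmol/L or more means interrupt, re-check within 72 hours and follow option b. For second and subsequent samples, option b has two rows. Below 5.5, the participant restarts at dose level 1. At 5.5 or more, the row reads "Continue to withhold study intervention, further monitoring of K" and allows restart at level 1 only below 5.0, with the restriction in bold capitals. Neither row depends on the dose level before the interruption.

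**Note 1 under Table 6-2.** For a participant already on level 1, "the same dose level should be re-started once serum/plasma potassium falls below 5.5 mmol/L". The note does not limit this to option a. Its second sentence asks for a potassium measurement at a safety visit 4 weeks ±7 days after restart or dose adjustment.

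**Protocol Section 7.1.1.** The scope is wide: "Upon temporary interruption of the study intervention due to hyperkalemia, eGFR decrease, (S)AE, outcome events (OE), intolerance or any other reason". It then says: "If the study intervention is interrupted for more than 7 days, the re-start should be performed at the next lower dose". It sets no maximum length of interruption, and the table it cites is Table 6-1, not Table 6-2.

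**Protocol Section 6.1 and Table 6-1.** Levels 1, 2 and 3 are 10, 20 and 40 mg. Level 3 is open only to participants with baseline eGFR above 60, whose starting dose is level 2. One step down from level 3 is level 2. For a level 1 participant who is interrupted, "study intervention should be re-introduced at dose level 1 as soon as the investigator considers it to be medically justified without compromising safety".

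**Cross-references.** Section 6.6 cites Sections 6.6.1 and 4.3 for the rule that "the dose of study intervention should be adjusted (up-or down-titration) on the basis of potassium and eGFR levels". Section 7.1 says "Note that study intervention may be temporarily discontinued (i.e. interrupted), as described in" Section 6.6. Section 8.2.3 says potassium is recorded "using a single decimal point (e.g. 4.5 mmol/L or mEq/L). In the event of hyperkalemia, please see" Table 6-2, and Section 10.2 points to Section 6.6.1. Section 4.1, on re-introducing drug after a temporary interruption, points instead to Sections 6.1 and 7.1.1.

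**The concern.** The benefit-risk argument in Protocol Section 2.3 relies in part on potassium-based rules for stopping and reducing study drug. The participants in question have already reached 6.0 mmol/L or more, so the restart rule is part of that safeguard.

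Two sites could each follow a written instruction and act differently on the same participant. A site working from Section 7.1.1 could restart a former 40 mg participant at twice the dose that Table 6-2 gives. A site working from note 1 could restart a level 1 participant at a potassium value at which option b, on its more natural reading, still withholds drug. What is at stake is consistency of dosing and a margin of safety on these pathways, not the analysis of the trial.

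**Working it through.** The plan states no figure to reproduce. The check applies each rule literally to the same participant and compares the results.

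**Restart dose after potassium of 6.0 or more and more than 7 days off drug**

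| Level before interruption | Table 6-2, option b | Section 7.1.1 (with Table 6-1) | Ratio |
|---|---|---|---|
| 3 (40 mg) | level 1, 10 mg | level 2, 20 mg | 20/10 = 2.0 |
| 2 (20 mg) | level 1, 10 mg | level 1, 10 mg | 10/10 = 1.0 |
| 1 (10 mg) | level 1, 10 mg | no lower level; Table 6-1 gives level 1, 10 mg | 10/10 = 1.0 |

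The rules differ at one of three dose levels. At 7 days or less the next-lower-dose rule in Section 7.1.1 does not apply, so nothing conflicts. More than 7 days off drug is possible because no maximum is set and option b can require potassium to fall from 6.0 or more to below 5.0.

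**Restart threshold at dose level 1 after potassium of 6.0 or more**

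Potassium is recorded to one decimal place (Section 8.2.3), so the values can be listed.

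- *Second sample.* Option b restarts below 5.5, and so does note 1. Differences: 0.
- *Third or later sample after a re-check of 5.5 or more, with the 5.0 limit carried forward.* Option b restarts below 5.0; note 1 restarts below 5.5. They differ at 5.0, 5.1, 5.2, 5.3 and 5.4, which is 5 values.
- *Third or later sample, each read afresh against the two option b rows.* Any value below 5.5 falls in the first row, so both rules restart. Differences: 0. On this reading the limit of 5.0 never operates, because a value below 5.0 already meets the first row.

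Note 1 concerns only participants already on level 1, so it creates no threshold difference at levels 2 or 3.

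The dose conflict therefore follows directly from the wording. The threshold conflict depends on giving effect to the capitalised 5.0 limit.

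**The case against.** The strongest reply has four parts.

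1. **The specific rule should beat the general one.** Section 7.1.1 covers every reason for interruption, while Table 6-2 addresses potassium of 6.0 or more. Sections 6.6, 7.1, 8.2.3 and 10.2 all direct potassium-related dosing or interruptions to Section 6.6 or Table 6-2. This favours Table 6-2 as the intended rule. It does not settle the matter: Section 7.1.1 names hyperkalemia, Section 4.1 sends restarts to Sections 6.1 and 7.1.1, and no text states precedence.

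2. **Note 1 was probably written for option a.** Its remark that no further reduction is possible matches the row for 5.5 to below 6.0, where a level 1 participant is interrupted because there is no lower dose. Option a's instruction to continue the current dose does not fit such a participant, so the note fills a real gap. The table's block for second and subsequent samples also permits the reading that gives no difference. Both arguments have force, which is why the threshold point is conditional. They do not change the fact that the note is unrestricted.

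3. **Investigators have discretion.** Table 6-2 is headed as guidance, Section 7.1.1 leaves the timing of resumption to the investigator, and note 3 allows further measures. A reader might infer that the protocol compels an unsafe restart; it does not. But discretion does not tell a site which written rule to follow.

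4. **The exposure is small.** Potassium of 5.0 to below 5.5 is a band in which Table 6-2 continues the current dose at a first sample, and 20 mg is the starting dose of the group concerned. Restart is followed by checks under note 1, footnote c to the Schedule of Activities and Section 7.1.1. SAP Section 6.4.1 describes hospitalization or permanent discontinuation for hyperkalemia as very infrequent. That is not a count of these pathways, but it bears on clinical impact. This part stands and limits the severity.

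**Conclusion.** A minor drafting inconsistency in dosing safety, to be corrected. The restart-dose conflict is clear: 10 mg against 20 mg for a level 3 participant interrupted for potassium of 6.0 or more and off drug for more than 7 days. The threshold conflict is conditional: five recordable values, 5.0 to 5.4, at level 1 only and from the third sample on, if the 5.0 limit is to have any effect.

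Three stronger conclusions might be drawn, and the documents do not support them. One is that a level 1 participant has no defined restart dose under Section 7.1.1; Table 6-1 supplies it. Another is that the potassium stopping rules fail as a safeguard; interruption at 6.0 or more is unambiguous, and restart remains subject to judgement and monitoring. The third is that the trial's inference is affected; no power, alpha or estimand figure changes.

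The documents do not say how often these pathways occur. The verdict applies to Amendment 2 (16 MAY 2022). The SAP relies on a protocol dated 26 OCT 2022 that was not supplied and may already have changed the text.

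**What to change.** First confirm whether the 26 OCT 2022 protocol still carries this wording. If it does, make three changes:

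- **Section 7.1.1:** add that after an interruption for potassium of 6.0 mmol/L or more, Table 6-2 governs and restart is at dose level 1.
- **Note 1:** limit only the first sentence to option a interruptions (first potassium 5.5 to below 6.0). Keep the second sentence, the potassium check 4 weeks ±7 days after restart, for all restarts. Narrowing the whole note would remove that check for option b restarts within 7 days, which footnote c does not cover.
- **Table 6-2, option b, row for 5.5 or more:** state that the limit of 5.0 applies to all later samples.

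These keep the stricter rule each time. That is a clinical choice for the sponsor: raising the table's limit to 5.5 would also remove the threshold conflict. The cost is a clarification letter or amendment text and a message to sites. The downside is that a few participants would restart slightly later or at a lower dose.
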